2. INTRODUCTION

Mental health problems are estimated to affect 10-20% of children and adolescents worldwide. Research shows that the prevalence of depression rises sharply after puberty and that over half of depressed adolescents have a recurrent episode within five years.

Mental health literacy can be defined as knowledge and beliefs about mental disorders which help people to prevent, recognise and manage problems. We know that low levels of mental health literacy significantly increase the risk of adolescents developing moderate to severe depression and that improving mental health literacy may be a useful way to reduce the future burden of depression amongst young people.

We have co-adapted with young people, parents, professionals and other stakeholders an existing interactive digital application, originally developed in Indonesia with MRC funding (IMPeTUs MR/R012741/1), to improve mental health literacy and self-management skills, for use in the UK with young people aged 12-14. We have also co-designed an additional third book designed specifically for young people in the UK.

The IMPeTUs intervention includes an immersive story line digital game in which young people play as two characters facing mental health challenges. Their decisions affect the direction of the game and eventual outcomes. This application will allow for UK specific intervention content to be developed and for associated materials to be co-produced with young people, parents, professionals and other stakeholders.

In the current study, we will test whether it is feasible to deliver and evaluate our intervention in education and community settings in the UK. We will randomly allocate 20 young people to receive our intervention and 20 to not receive it and then follow them up 3-months later. We will explore how many young people want to take part in our study (recruitment and retention), how much they use our intervention and what sort of follow-up data they are willing to provide. We will speak to facilitators (n=4-6), young people (n=10) and professionals (n=6-10) about their experiences of receiving and delivering our intervention and parents/guardians (n=6-10) about their their child's experiences with the intervention. We will use these findings to collaboratively design a larger study to explore the costs and impacts of our intervention.

We have appointed a PPI advisory panel and implementation reference group to oversee our project and will work with young people and those with experience of mental health difficulties in the delivery of study activities. We will use different ways (e.g. leaflets, social-media, journal articles, animations/podcasts) to tell young people, families, professionals and communities about our work.

3. BACKGROUND

Mental health problems are a major global public health issue. Common mental health problems such as anxiety and depression, account for 13% of the global burden of disease and affect

Version: 2 Date: 11/7/2022 UREC ID: 2022-14361-24300

approximately 10–20% of children and young people (CYP) worldwide [1]. Population studies show that the prevalence of depression rises sharply after puberty, and 50-70% of depressed CYP have a recurrent episode within five years [2]. CYP onset is associated with depression in adulthood, poorer physical health and functioning across the lifespan, and increased suicide risk [3].

Approximately half of all mental health disorders begin by the age of 14 [4]. The impact of mental ill health is significant across the life course contributing to poorer social and physical health outcomes, premature mortality, and economic burden [3]. In England, one in eight children (13%) aged 5-19 have a mental disorder [5]. Further, the percentage of young people with a probable mental health disorder has increased by approximately 6% between 2017-2020, likely an impact of COVID-19 [6].

Rates of under-recognition and under-treatment of depression are higher in CYP than in adults, resulting in poorer clinical and social outcomes [7]. Seventy percent of young people experiencing mental health difficulties in high income countries do not receive evidence-based treatment at an appropriate age [8]. In the UK, mental ill health is the largest cause of disability contributing up to 22.8% of the total burden, a greater health burden than other major health diseases [9]. The cost of mental ill health is estimated to be in excess of £16 billion for depression and anxiety alone. This economic burden is also rising exponentially. Pre-pandemic analyses projected the total societal costs of depression to reach US\$ 16.0 trillion by 2030, a cost comparable to that of cardiovascular disease [10]. Emerging data suggest an additional post-pandemic increase in burden and treatment need among young people [6].

Improving the mental health of children and young people is a national and international imperative [11-12]. It is also a national research priority, with the James Lind Alliance setting 10 specific priority areas for mental health in children and young people including a focus on mental resilience and identifying what self-help and self-management resources work [13].

COVID-19 has significantly impacted on the mental health of children and young people. There are a myriad of government/policy, third sector/VCSE and academic reports published signaling the concern for mental health and well-being among adults and young people [14-16]. While the focus on transforming services to meet the needs of young people with poor mental health has been a policy imperative in the UK since 2015 [17], the pandemic has highlighted and exacerbated the gap between the needs of young people and the solutions on offer. The current pandemic presents an opportunity to develop preventative solutions which are cost-effective in the short-and longer term. Such solutions have the potential to support young people today to become healthier future generations of adults [18-20].

Mental health literacy (MHL) is defined as 'knowledge and beliefs about mental disorders which aid their recognition, management or prevention.' It includes i) the ability to recognise disorders; ii) awareness of the types of professional help and treatments available, iii) knowledge of effective self-help strategies; iv) knowledge and skills to give 'first-aid' and support to others; and v) knowledge of how to promote mental wellbeing and prevent mental health disorders [21]. In adults, low levels of mental health literacy have been found to be associated with higher rates of

Version: 2 Date: 11/7/2022 UREC ID: 2022-14361-24300

mortality [22]. Systematic reviews examining the effectiveness of mental health literacy interventions for adolescents demonstrate their potential value as health promotion and prevention tools [23-24].

Inadequate mental health literacy in adolescents significantly increases the risk of developing moderate-severe depression [25]. Encouragingly, adolescents demonstrate a strong preference for peer and family support over professional support, suggesting that universal mental health literacy programs may have benefits for both primary and secondary disease prevention [26]. School-based psycho-educational interventions are effective in reducing stigma, promoting young peoples' mental health knowledge, and increasing mental health literacy but require but rely on educational engagement, leadership and delivery support at a local level [27]. There is a dearth of co-produced and self-directed digital mental health literacy interventions for young people in the UK.

Overview of the technology: Stepped care prevention and treatment approaches, where psychological interventions are delivered in different steps according to need, are considered an optimal solution to reduce the burden on health systems [28]. Our solution is a mental health prevention intervention designed to reduce the burden on health systems through better self-management of mental health and timely intervention through improved recognition and effective help-seeking.

We have co-adapted and extended an interactive resource, originally developed in Indonesia with MRC funding (IMPeTUs MR/R012741/1), for use in school and community health settings in the UK. We have co-produced training materials for facilitators, educational materials for parents, and implementation resources.

The IMPeTUs intervention includes an immersive story line digital game for CYP in which children play as a character facing mental health challenges [28]. Their decisions affect the direction of the game and outcomes. The storyline format is interspersed with interactive games and activities to promote engagement and support the development of self-help strategies. CYP also participate in facilitated group discussions before and after playing the game to enable discussions about the issues raised in the game. Our preparator work has allowed for the existing intervention content to be adapted for use in the UK and for additional material to be co-produced with CYP, parents, professionals and other stakeholders. This includes an additional intervention book, a training toolkit and evidence-based implementation strategy to optimise use in the UK.

Version: 2 Date: 11/7/2022 UREC ID: 2022-14361-24300 Figure 1: Screenshots of interactive elements of the intervention

Proof of concept for our candidate intervention comes from Patient and Public Involvement (PPI) feedback in the co-design and initial testing (n=8) and evidence from 9 ongoing case study evaluations (n=90 CYP) which suggests our intervention is accessible, acceptable, and implementable to CYP. A theory of change underpinning the current intervention can be found in Figure 1.

Version: 2 Date: 11/7/2022 UREC ID: 2022-14361-24300

Figure 1: Theory of change

We have co-adapted this intervention for use with UK adolescents and will co-produce a protocol for definitive evaluation of our intervention. This will include a randomised control trial and mixed method process evaluation to evaluate the clinical and cost effectiveness of our intervention in line with MRC guidelines for the evaluation of complex interventions.

Value proposition - Benefits to patients and the healthcare system: Our co-adapted intervention is evidence based, co-produced and developmentally appropriate. These features of intervention development maximise the likelihood of implementation effectiveness amongst UK adolescents aged 12-14. This age range was chosen as a direct result of PPI activities undertaken as part of the development of this grant. This age range corresponds to key stage 3 in the UK educational system, is pre-exam curriculum stage and is also relevant in terms of mental illness prevention as the peak period of onset is in the mid to late teens.

Conceptual frameworks identify health literacy as a critical mediator of health and functional outcomes [30]. Systematic reviews and effectiveness studies demonstrate that mental health promotion interventions, when implemented effectively, can have lasting, positive effects on health [31,32]. Longitudinal, population-based cohorts (N=7857) have demonstrated a relationship between lower mental health literacy and higher mortality rates in older adults [22] and identified mental health literacy as a significant predictor of psychological and pharmacological treatment engagement [33]. Reductions in morbidity and mortality will be mediated by individual, social and system-level variables, especially those that increase health behaviour and/or health service engagement.

Version: 2 Date: 11/7/2022 UREC ID: 2022-14361-24300

MHL skills have consistently been shown to be associated with improved health outcomes and social determinants of health. The available evidence suggests improved recognition and knowledge about mental illness and appropriate help can improve help seeking in children and young people. This is important given studies show that as little as one third of adolescents seek appropriate treatment for mental health problems; timely and appropriate help seeking in early adolescence is critical given its association with reduced likelihood of mental disorder in later older adolescence and later life [34]. Further, poorer MHL has been associated with increasing mental illness among adolescents [35].

Adolescents express preference for peer and family/community support rather than professionally led services which indicates that our intervention may have considerable benefit for improving MHL [26]. There is good evidence to indicate components of effective digitally delivered interventions include active ingredients such as tailoring to specific populations, evidence-based content, video illustration, quizzes and other interactive features [36]. The design of the current MHL intervention is based on these components of effective engagement and digital implementation.

The project will produce freely available evidence-based guidance to maximise widespread adoption, implementation and reach for communities. This will include guidance on the universal and culturally specific features of the MHL intervention to support co-adaption of the intervention for other high-income and low-income communities according to local population needs. We will work with local health and care partners to make resources available via existing networks, including training and best practice knowledge hubs to encourage wide roll-out of the programme deliverables.

The focus of our MHL intervention is prevention, building community capacity, reducing health inequalities and better mental health. These align with Public Health England strategy priorities (2020-2025) [37]; therefore we will be well placed to submit an application to NIHR Public Health Research funding streams. The current application will assure funders that we have developed an optimal strategy for implementation and definitive evaluation to embed and sustain the intervention.

4. STUDY OBJECTIVES

Aim: To evaluate the feasibility/acceptability of an RCT to assess the clinical and cost effectiveness of our co-adapted intervention.

Objectives:

- To train 4-6 facilitators to deliver our co-adapted intervention.
- To recruit 40 young people (four groups of ten, across four sites) to participate in a trial to evaluate the feasibility of a cluster-randomised controlled trial to determine the clinical and cost-effectiveness of our intervention by quantifying participant recruitment, retention and 3-month follow up rates.
- To determine intervention acceptability and identify from multiple stakeholder perspectives the barriers and facilitators to implementation.

Version: 2 Date: 11/7/2022 UREC ID: 2022-14361-24300

- To examine the applicability (content-validity) and acceptability (full and partial completion rates, sensitivity to change) of proposed trial outcome measures and the need for additional CYP prioritised outcomes.
- To collect outcome data to inform parameters for a fully-powered trial, including the identification and standard deviation of the proposed outcomes measure needed to estimate trial sample size.
- To co-produce with stakeholders a protocol for definitive evaluation of our intervention.

5. STUDY DESIGN AND PROTOCOL

The MRC recommends feasibility testing to ensure new interventions can be implemented prior to undertaking definitive evaluations through fully powered randomised controlled trials [44].

Design: A multi-site, cluster-randomised feasibility trial with nested process evaluation.

Target population: 40 CYP aged 12-14, attending school and community settings (study sites) in Greater Manchester. This age range was chosen following PPI consultation as it corresponds to key stage 3 in the UK educational system, is pre-exam curriculum stage and is relevant in terms of mental illness prevention as the peak period of onset is in the mid to late teens. Parents/guardians (n=6-10), professionals (n=6-10) and facilitators (n=4-6) will also participate alongside CYP participants in the nested process evaluation.

Participants must have capacity to consent (checked at each assessment point) and be able to read and write in English to engage with study materials. Translation of materials is not possible in the current study but will be prioritised in a future study should our intervention show promise. CYP participants need to have access to a smartphone/tablet to use the intervention.

Setting: Education and community settings in Greater Manchester.

Sample size: Our feasibility trial will not formally test intervention effect so a formal power calculation is not appropriate. Instead, sample size has been selected to allow us to assess key feasibility outcomes (recruitment, retention, intervention uptake) and to allow sufficient replications of the study protocol to highlight barriers to completion in the main trial. The sample size will also allow us to estimate differences in means for intervention outcomes to within 0.25 standard deviations.

Recruitment: Four sites (schools/ community venues) will be recruited to the study. All eligible CYP in participating sites will be invited to take part. Educational professionals and community leaders (facilitators) will issue study information to potential participants and obtain CYP assent and parental consent and contact information and collect CYP baseline measures. Direct invitations and information sheets will be available at participating sites so that interested participants can enquire about the study directly.

Randomisation: In this study, an equal number of clusters (two per arm) will be allocated to the intervention and control arms. This will be achieved by using a blocked randomisation list. The study statistician will produce the randomisation list. A cluster will not be allocated until the full set of 10 participants have been recruited at that cluster, to prevent allocation bias. The allocation

Version: 2 Date: 11/7/2022 UREC ID: 2022-14361-24300

sequence will not be revealed to the other study investigators. Outcome data will predominantly be self-report.

Intervention: Our intervention combines an interactive individual game in conjunction with prepost facilitated group discussions. Our candidate intervention will be co-adapted in phase 1 and additional content and materials co-produced with a range of stakeholders including CYP, parents, professionals and community members.

Group-delivery is a low-cost delivery model which can derive additional benefits through peer-topeer support. Systematic review and meta-analysis [49-50] suggests that engaging students in activities such as games, simulations and group work is more effective than relying solely on didactic methods. We will align the structure of our intervention with current evidence [51-53] supporting the effectiveness of short-term programmes for mental health education and mental health first-aid. Frequency, duration and content of the intervention will be recorded by facilitators and reviewed in phase 2 facilitator and CYP interviews to explore whether treatment was delivered as intended.

Minimum levels of intervention require engagement in each of the chapters of the intervention for a minimum of 1 h each and participation in a facilitated group session before and after the intervention (minimum 5-6 hours in total).

The intervention will provide a range of techniques to improve mental health literacy and promote self-management, e.g. cognitive reframing, distraction and/or the substitution of more adaptive behaviours. Intervention content will be standardised via a manual. Intervention facilitators health and community workers will be trained by a multidisciplinary team, comprising co-applicants [name], [name] and a PPI representative.

Fidelity: Frequency, amount and content of the intervention will be recorded by the facilitators and reviewed in CYP interviews to explore whether treatment is delivered as intended.

Comparator: Our comparator is assessment only. We will ascertain the range and variability in usual care. The frequency, amount and type of health services accessed by intervention and control arm participants will also be recorded. The control group will be offered access to the intervention at study end.

Feasibility outcomes: The primary outcomes are feasibility outcomes. We will assess CYP recruitment and retention rates, intervention uptake and engagement rates, and the variability and potential floor/ceiling effects in our proposed patient outcome measures. CYP outcomes will be measured as baseline (prior to randomisation), post-intervention (or at approximately 6 weeks post-randomisation for control group participants) and 3-month follow-up.

Clinical outcomes: The primary clinical outcome measure will be a version of the mental health literacy scale, the Knowledge and Attitudes to Mental Health Scale (KAMHS). Additional measures will include the short version of the Mood and Feeling Questionnaire (MFQ), the World Health Organisation Five Well-Being Index (WHO-5), the Revised Children's Anxiety and Depression Scale (RCADS), the Family Cohesion and Satisfaction with Communication subscales of the Family Adaptability and Cohesion Evaluation Scale (FACESIV), and the SF-36

Version: 2 Date: 11/7/2022 UREC ID: 2022-14361-24300

quality of life questionnaire. We will assess the feasibility of these different outcome measures as part of our feasibility trial.

At baseline, CYP demographics and psychiatric history will be recorded.

Analysis: As this is a feasibility trial, analysis will be mostly descriptive.

We will identify the number of study referrals, consents to research contact, and calculate cumulative and monthly recruitment rates. We will examine referral and recruitment rates between different sites (e.g. education and community settings) and recruitment routes (e.g. professional or self-referral).

The proportions of target sample size achieved, of participants who start and engage in the intervention, and the proportion retained in the study and providing outcome data will be calculated. Descriptive statistics will assess the completeness and variability of participant and cost outcome measures at each point.

We will undertake exploratory comparisons of intervention outcomes on an intention-to-treat basis, recognising that these analyses will be underpowered. These will focus on plausible ranges for effect sizes as indicated by 95% confidence intervals, and will be analysed with adjustment for the corresponding baseline measure of the outcome, in order to improve precision. We will attempt to control for clustering in this analysis by including a random intercept in a mixed model, although the small sample size may prove prohibitive. If this analysis can not be realised, we will adjust for site as a fixed effect. We will also present an adjusted mean difference (95% CI) based on ANCOVA (adjusted for corresponding baseline value of the outcome, with no adjustment for site).

Feasibility success criteria: See success criteria outlined below:

Progression criterion: Willingness of participants to be randomised

- Red: Recruit < 60% of required sample.
- Amber: Recruit 60-80% of required sample.
- Green: Recruitment > 80%.

Progression criterion: Retention in intervention arm

Participants will be considered retained in the intervention arm if they are available for assessment at 3 month follow-up.

- Red: Retain < 60% of participants in the intervention arm at 3-month follow-up
- Amber: Retain 60-80% of participants in the intervention arm at 3-month follow-up
- Green: Retain > 80% of participants in the intervention arm at 3-month follow-up.

Progression criteria: Uptake of intervention

Participants will be considered to have suitably engaged with the intervention if they take part in each of the chapters of the intervention for a minimum of 1 h each and participate in a facilitated group session before and after the intervention (minimum 5-6 hours in total).

Version: 2 Date: 11/7/2022 UREC ID: 2022-14361-24300

- Red: Engage <60% of participants at the requisite level described above.
- Amber: Engage 60-80% of participants at the requisite level described above.
- Green: Engage >80% of participants at the requisite level described above.

Process Evaluation: We will use the MRC process evaluation model [44] to explore the delivery and reach of our intervention and understand barriers/enablers to roll-out.

Qualitative interviews 1-2 months post-intervention will explore the acceptability of trial procedures and the feasibility of our intervention with CYP, parents/guardians, professionals and facilitators. Interview schedules will be informed by the Theoretical Framework of Intervention Acceptability (TFA) [55] and the Consolidated Framework for Implementation Research (CFIR) [56].

Purposeful maximum variation techniques will be used to sample trained intervention facilitators (n=4-6), parents/guardians (n=6-10), CYP (n=10) and relevant professionals (n=6-10). Maximum variation sampling will ensure participants of different ages, genders, baseline scores and outcome are included.

Interviews will be digitally recorded, transcribed verbatim and analysed using Framework Analysis, with coding undertaken blind to trial outcomes. Analysis will encompass inductive and deductive coding informed by NPT and CFIR.

We will host a one-day workshop with our PPI advisory panel, to synthesise learning and revise our preliminary theory of change and use this to guide intervention refinement and optimise referral and evaluation protocols.

Patient and public involvement: We have consulted project partners and engaged 8 young people in a group discussion to inform the development of our application. CYP felt strongly that the age range for our intervention should be reduced from 11-16 in our original expression of interest to 12-14 in the current application as they felt it would not be possible to produce an intervention which was developmentally appropriate and sufficiently engaging for all CYP aged 11-16. Participatory discussion also confirmed that many young people have little or no contact with health services and may not be regularly attending education institutes. Optimal recruitment strategies for phase 2 will be collaboratively derived with attendees at phase 1 workshops. We also embedded multiple engagement strategies (social media, community advertising, online resources) to generate interest in our study and maximise study deliverables in line with CYP feedback. Our proposed PPI advisory group chair led the design and delivery of our 3-minute video pitch.

We will draw on our experience to develop patient and public involvement (PPI) informed by NIHR Involve guidelines including:

- a track record of PPI in mental health research;
- an award-winning profile for innovative co-production;
- established links with community networks including underserved groups in Greater Manchester.

The University of ManchesterVersion: 2 Date: 11/7/2022 UREC ID: 2022-14361-24300Our strategy is underpinned by the standards set out in the UK Standards for Public Involvementin Research framework (https://sites.google.com/nihr.ac.uk/pi-standards/standards).

We will establish a PPI advisory panel comprising key stakeholders e.g. CYP, carers, health and education policy leads and professionals, VCSE representatives. Based on prior experience, 2 sub-panels will be established: one for young people and one for adults (n=5-6/each). Sub-panels will meet quarterly. To facilitate communication, a member of the young person's panel will attend adult meetings.

Advisory panel members will receive an induction, supplemented throughout the project with support from the research team, and peer-support through PPI meetings/ad hoc arrangements. All PPI representatives will be linked with local support networks and training and development opportunities.

Optimising inclusivity and diversity requires acknowledgement of the under-representation of ethnic minorities, women and other minority groups. We have adopted an integrated participatory approach to ensure diversity in study design, participation and partnership working. We will work directly with CEI collaborators and advisory groups to identify and overcome barriers that may restrict engagement and participation in research by different groups. Our core team, specialist collaborators and project partners have access to a wide range of CYP/family networks and Third Sector organisations working directly with underserved groups. Two members of our CEI advisory group will be elected to act as Equality and Diversity champions.

We will identify service-user researchers to contribute to qualitative and quantitative research, and lead meetings on intervention development and intervention co-adaptation. Research training and mentorship will be provided to CYP (e.g. qualitative research). [name], [name], [name] have led NIHR and MRC programmes developing and delivering research education for MH service-users and carers. The course is cited as good practice and included in the NICE shared learning database. It has been adapted and implemented amongst CYP PPI contributors in the UK.

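### Twenty participants per arm cannot estimate differences in means to within 0.25 SD: the 95% half-width is about 0.64 SD unadjusted with clustering ignored, and wider once the four sites are respected

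*Protocol*

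**What the plan says.** The Sample size paragraph of Protocol Section 5 declines a formal power calculation, because no formal test of effect is planned. It says the number was chosen to assess recruitment, retention and uptake and to rehearse the study procedures. It then adds one quantitative statement: "The sample size will also allow us to estimate differences in means for intervention outcomes to within 0.25 standard deviations".

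The design facts that bear on this figure are:

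- Section 2 (Introduction): "We will randomly allocate 20 young people to receive our intervention and 20 to not receive it".
- Section 5, Design: "A multi-site, cluster-randomised feasibility trial with nested process evaluation".
- Section 5, Randomisation: "an equal number of clusters (two per arm) will be allocated to the intervention and control arms". Section 4 gives four groups of ten, one at each of four sites.
- Section 5, Analysis, on the exploratory outcome comparisons: "These will focus on plausible ranges for effect sizes as indicated by 95% confidence intervals", with "adjustment for the corresponding baseline measure of the outcome, in order to improve precision".

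The Analysis text also concedes that these comparisons will be underpowered. It plans a random intercept for site if the small sample allows, a fixed site effect if not, and in addition a baseline-adjusted ANCOVA with no site term.

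**The concern.** A claim to estimate a difference to within a stated margin is ordinarily read as a confidence-interval half-width, and the protocol's own analysis text supplies the 95% level. Twenty per arm is far too few for a margin of 0.25 SD at that level, and four randomised sites make it harder still.

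The sentence is the only number offered in support of the sample size. A reader who takes it at face value would expect the exploratory estimates to be much sharper than they can be. It also sits badly with the admission that the comparisons are underpowered. A true 95% half-width of 0.25 SD implies a standard error of 0.25/1.96 = 0.128 SD, and hence 80% power for a difference of (1.96 + 0.84) × 0.128 = 0.36 SD. Few would call that underpowered.

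**Working it through.** **Inputs from the protocol.** 20 per arm (Section 2); four sites of ten (Section 4); two sites per arm (Section 5, Randomisation); two-sided 95% intervals and baseline adjustment (Section 5, Analysis).

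**Inputs not given, so assumed.** Baseline correlation r of 0.5, 0.7 or 0.8; ICC from 0 to 0.05; full retention unless stated. Results are in units of the outcome SD.

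**1. Trying to reproduce 0.25 SD.**

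Unadjusted, with clustering ignored, SE = sqrt(2/20) = 0.316.

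- Normal half-widths are 0.41 at 80% confidence, 0.52 at 90% and 0.62 at 95%.
- A margin of 0.25 gives 0.25/0.316 = 0.79 standard errors, which is about 57% confidence (unadjusted and unclustered).
- Other targets do not match at 95% either: a single-arm mean has 1.96/sqrt(20) = 0.44, and the mean of all 40 has 1.96/sqrt(40) = 0.31.
- One reading does reach 0.25: a single standard error after baseline adjustment with clustering ignored. Setting 0.316 × sqrt(1 − r²) = 0.25 gives r = sqrt(1 − 0.625) = 0.61. That is one standard error, not a 95% margin.

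**2. 95% half-width, clustering ignored.**

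- Unadjusted: t(38) × SE = 2.024 × 0.316 = 0.64.
- Baseline-adjusted: t(37) × SE × sqrt(1 − r²), with t(37) = 2.026.

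| Assumed r | sqrt(1 − r²) | 95% half-width |
|---|---|---|
| 0.5 | 0.866 | 0.55 |
| 0.7 | 0.714 | 0.46 |
| 0.8 | 0.600 | 0.38 |

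- Correlation needed for 0.25: sqrt(1 − (0.25/(2.026 × 0.316))²) = 0.92.
- Sample needed for 0.25 unadjusted: 2 × (1.96/0.25)² = 123 per arm, even with independent observations.
- With 16 per arm (80% of 20 retained), unadjusted: 2.042 × sqrt(2/16) = 0.72.

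**3. 95% half-width, respecting the sites.**

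Four sites less two arms leave 2 degrees of freedom, and t(2) = 4.303. The design effect is 1 + (10 − 1) × ICC, and SE = sqrt(2 × design effect/20). The adjusted columns multiply by sqrt(1 − r²), which assumes that baseline adjustment reduces variance by the same proportion within and between sites.

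| Assumed ICC | Design effect | SE | Unadjusted | r = 0.5 | r = 0.7 |
|---|---|---|---|---|---|
| 0 | 1.00 | 0.316 | 1.36 | 1.18 | 0.97 |
| 0.01 | 1.09 | 0.330 | 1.42 | 1.23 | 1.01 |
| 0.02 | 1.18 | 0.344 | 1.48 | 1.28 | 1.06 |
| 0.05 | 1.45 | 0.381 | 1.64 | 1.42 | 1.17 |

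Most of the widening comes from the 2 degrees of freedom. At ICC 0.05, the design effect with a normal multiplier gives only 1.96 × 0.381 = 0.75. With 8 retained per site, the unadjusted range for ICC 0 to 0.05 becomes 1.52 to 1.77.

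**The case against.** Several points can be made for the protocol, and some of them stand.

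- **The statement is secondary.** This stands. The sample size is tied first to feasibility outcomes, which are primary; no formal test is planned; and no progression criterion uses a between-arm difference. A reader might infer that the choice of 40 is unsupported or must rise. The protocol does not support that, because its stated reasons for 40 do not depend on the 0.25 figure.
- **The protocol already calls the comparisons underpowered.** True, and it softens the harm. But the remark gives no number and does not withdraw the 0.25 SD.
- **No confidence level is attached, so 0.25 might be a standard error.** The 95% reading is an inference, though a natural one given the analysis text. A reader might infer that the standard error exceeds 0.25 SD on any reading. That holds only without adjustment or with a baseline correlation below about 0.61. Above that, one standard error with clustering ignored is within 0.25, but the sentence would then be unclear and would still omit clustering.
- **The site-level figures depend on method.** This stands. A reader might take 1.4 to 1.6 SD as simply the precision of this trial. It needs an unadjusted site-level analysis on 2 degrees of freedom, full retention and an ICC that the protocol does not give. The protocol plans baseline adjustment and a mixed model, and names no degrees-of-freedom method.
- **No misuse is planned.** A reader might infer that the observed difference will set the target effect for the main trial. Section 4 names outcome identification and the standard deviation for that purpose, and does not mention the observed difference.

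**Conclusion.** The 0.25 SD figure is wrong as a 95% precision statement for 20 per arm.

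- **Clustering ignored:** the half-width is 2.6 times the stated figure unadjusted (0.64/0.25), 2.2 times at an assumed correlation of 0.5 and 1.8 times at 0.7. Only a correlation of about 0.92 would rescue it.
- **Sites respected:** at an ICC of 0 to 0.05 with full retention and 2 degrees of freedom, it is roughly 5.4 to 6.6 times unadjusted (1.36 to 1.64 SD), and 4.7 to 5.7 times with adjustment at a correlation of 0.5 (1.18 to 1.42 SD).

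The unadjusted, unclustered result rests only on the protocol's own numbers and its 95% level. The others rest on the stated assumptions about correlation, ICC, degrees of freedom and retention. The sentence needs correcting, but the error leaves the feasibility outcomes, the progression criteria and the sample of 40 untouched.

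**What to change.** Keep 40 participants. Either delete the sentence in the Sample size paragraph of Section 5, or replace it with the achievable 95% half-width and the assumptions behind it: baseline correlation, ICC, degrees of freedom and retention. Suitable wording would be:

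*With 20 participants per arm, full retention and clustering ignored, the 95% confidence interval for a difference in means will have a half-width of about 0.64 SD unadjusted, or about 0.55 SD if the correlation with baseline is 0.5. Allowing for randomisation of two sites per arm (site-level analysis, 2 degrees of freedom, assumed ICC 0 to 0.05, full retention), the half-width is about 1.36 to 1.64 SD unadjusted, or about 1.18 to 1.42 SD if adjustment at that correlation reduces variance at both levels.*

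The cost is a change of protocol wording. Recruitment, randomisation, planned analyses and progression criteria stay as they are; only the stated precision becomes less favourable.
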